#### **4.1.8 Neuropathology Core**

The LEADS Neuropathology Core comprises three hub sites that will oversee organization of participating clinical sites. The three hub sites are located at Indiana University, University of California, San Francisco, and Mayo Clinic Jacksonville. The three hub sites coordinate autopsies at participating sites and perform clinicopathologic analyses on EOAD and EOnonAD brain tissue. The Neuropathology Core leaders will support the clinical sites, collaborate with LEADS investigators, organize and participate in consensus-building activities, and lead tissue-sharing efforts. The Neuropathology Core will fulfill the following goals: 1) Facilitate and secure brain procurement at the time of death from all LEADS participants; 2) Conduct thorough, uniform postmortem neuropathologic examinations and assign all appropriate diagnoses for each case and contribute neuropathologic data to the NACC database (including diagnoses, accurate staging, and semiquantitative assessments of distribution and density of neuropathologic lesions); 3) Maintain a resource of formalin-fixed brain tissue blocks for LEADS investigators and outside investigators with an updated database of frozen tissue location and availability; and, 4) Review tissue requests by committee and provide samples and data to qualified investigators.

#### **4.2 End of Study Definition**

Given the overarching goal of the study to advance our knowledge and facilitate implementation in clinical trials with this unique cohort, there is no specific end point. Study activities are anticipated to continue until funding is no longer available.

### **5.0 STUDY POPULATION**

#### **5.1 Inclusion Criteria**

##### Cognitively impaired (EOAD and EOnonAD) Cohorts Only:

1. Meets NIA-AA criteria for MCI due to AD or probable AD dementia
2. Have a global CDR score  $\leq 1.0$
3. Have capacity to provide informed consent (IC) or has a legal authorized representative or guardian who provides IC
4. Age between 40-64 years (inclusive) at the time of consent
5. Must have a study partner (informant) who spends a minimum average of 10 hours per week with the participant (e.g., family member, significant other, friend, caregiver) who is generally aware of the participants' daily activities and can provide information about the participant's cognitive and functional performance. If the participant does not have a study partner who spends at least 10 face-to-face hours per week, other arrangements for identifying a viable study partner will be granted on a case-by-case basis by the Site PI
6. Willing and able to complete longitudinal study procedures aside from LP which is an optional procedure
7. Not pregnant or lactating. Women must be two years post-menopausal, be surgically sterile, or have a negative pregnancy test prior to each PET scan
8. Fluent in English or Spanish if enrolled in the U.S.
9. Fluent in English, Spanish, Dutch or Swedish for sites outside the U.S., according to site's spoken language(s).

##### Cognitively Normal (CN) Cohort Only:

1. Meets criteria for cognitively normal, based on an absence of significant impairment in cognitive functions or activities of daily living
2. Have a global CDR score = 0
3. Have capacity to provide informed consent
4. Have a Mini-Mental State Exam score between 26-30 (inclusive). Exceptions may be made for participant with less than 8 years of education at the discretion of the Site PI
5. Age between 40-64 years (inclusive) at the time of consent
6. Must have a study partner (informant) who spends a minimum average of 10 hours per week with the participant (e.g., family member, significant other, friend, caregiver) who is generally aware of the participants' daily activities and can provide information about the participant's cognitive and functional performance. If the participant does not have a study partner who spends 10 face-to-face hours per week, other arrangements for identifying a viable study partner will be granted on a case-by-case basis by the Site PI
7. Willing and able to complete longitudinal study procedures aside from LP which is an optional procedure
8. Not pregnant or lactating. Women must be two years post-menopausal, be surgically sterile, or have a negative pregnancy test prior to each PET scan
9. Fluent in English or Spanish if enrolled in the U.S.
10. Fluent in English, Spanish, Dutch or Swedish for sites outside the U.S., according to site's spoken language(s).

**Returning Participant (RP) Cohort Only:**

1. Must be a previous participant of LEADS that met initial eligibility criteria and completed a baseline visit
2. Have capacity to provide informed consent (IC) or has a legal authorized representative or guardian who provides IC
3. Must have a study partner (informant) who spends a minimum average of 10 hours per week with the participant (e.g., family member, significant other, friend, caregiver) who is generally aware of the participants' daily activities and can provide information about the participant's cognitive and functional performance. If the participant does not have a study partner who spends at least 10 face-to-face hours per week, other arrangements for identifying a viable study partner will be granted on a case-by-case basis by the Site PI

See section 8.8 for description of Returning Participants.

**5.2 Exclusion Criteria**

**EOAD, EOnonAD and CN Cohorts:**

1. Meets core clinical criteria for non-AD dementia
2. Two or more first degree relatives with a history of early-onset dementia suggestive of autosomal dominant transmission, unless known pathogenic mutations in *APP*, *PSEN1*, *PSEN2*, *MAPT*, *GRN* and *C9ORF72* have been excluded
3. Known CLIA certified mutation in an ADAD gene (*APP*, *PSEN1*, *PSEN2*), or other autosomal dominant genes associated with other neurodegenerative disorders (*MAPT*, *GRN*, *C9ORF72*)

4. Contraindications to 3T MRI (e.g., claustrophobia, pacemaker, select aneurismal clip, artificial heart valve, select ear implants, select stents incompatible with 3T MRI, metal fragments or foreign objects in the eyes, skin or body, etc.)
5. Lifetime medical history of a brain disorder other than the disorder causing dementia except for headache (exceptions are allowed at the discretion of the Site PI - e.g., seizure disorder thought to be due to EOAD).
6. MRI scan with evidence of infection or focal lesions, cortical strokes, multiple lacunes (single lacune is allowable unless it meets criteria for strategic lacune affecting cognition)
7. Any significant systemic illness or unstable medical condition, which could lead to difficulty complying with the protocol (at the discretion of the Site PI)
8. Research radiation exposure will be assessed by the study physician. If the candidate participant has had more than one nuclear medicine study in the prior 12 months for research-related purposes, study inclusion will require approval from the PET Core
9. Investigational agents are prohibited 30 days prior to entry
10. Previous enrollment in a therapeutic trial targeting amyloid or tau.
11. Participation in other clinical studies with neuropsychological measures, with the exception of participants who are co-enrolled in the NACC Uniform Data Set (UDS) protocol (Note: This criterion is intended to reduce repeat measures effects during neuropsychological testing. Exceptions are allowed at the discretion of the Site PI)
12. Lifetime history of schizophrenia spectrum disorders (DSM-5 criteria)
13. Current history (in previous 12 months) of DSM-5 diagnosis of mania, bipolar disorder with or without psychotic features
14. Current history (in previous 6 months) of moderate or severe substance abuse (nicotine or caffeine is allowed)
15. Suicidal behaviors in the past 12 months or active suicidal ideations
16. Residing in a 24-hour care skilled nursing facility (at the time of screening)
17. *(For optional lumbar puncture procedure only):*
  - a. Clinical laboratory values must be within normal limits or, if abnormal, must be judged to be not clinically significant by the Site PI
    - i. Platelet count <100,000/ml
    - ii. INR>1.2
    - iii. Abnormal PT or PTT at screening
  - b. Contraindications to the procedure, including but not limited to severe degenerative joint disease, deformity of the spine, history of a bleeding disorder
  - c. Suspected elevated intracranial pressure, Arnold Chiari malformation or mass lesion
  - d. Use of the anticoagulant medications such as but not limited to warfarin, rivaroxaban, dabigatran
18. Deemed ineligible by the Site PI for any other reason

RP Cohort:

1. Investigational agents are prohibited for five half-lives prior to study re-entry.

NOTE: Deviations from the inclusion/exclusion criteria will be considered with prior review and approval by the Site PI, the Clinical Core, and the IRB. Contact the ATRI Coordinating Center to request a review.

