## 1.0 BACKGROUND AND SIGNIFICANCE

While the risk of AD increases with advancing age, approximately 5% of AD patients develop symptoms before age 65 (~280,000 Americans). Patients with early-onset Alzheimer's disease (EOAD), occurring before the age of 65, are an understudied segment of the patient population with Alzheimer's Disease (AD). Many treatment studies exclude these younger individuals.

Of the two major North American consortia, ADNI includes only a few EOAD cases all with a “typical” amnestic presentation and the Dominantly Inherited Alzheimer Network (DIAN) focuses solely on autosomal dominant AD (ADAD). Clinical and neuroimaging measures that emphasize episodic memory and medial temporal neurodegeneration in

LOAD are insensitive to the baseline deficits and the disease progression in EOAD, which predominantly involve non-memory cognitive domains and posterior cortical neurodegeneration. The overarching aim of this Longitudinal Early-Onset AD Study (LEADS) is to fill this gap in AD research by conducting a clinical and biomarker study in the EOAD population.

LEADS includes key AD research sites across the U.S. and will leverage existing infrastructure and processes applied in ADNI. The over-arching goals are to advance our knowledge about disease mechanisms and develop sensitive composite clinical and biomarker tools that capture disease progression in this unique cohort for implementation in clinical trials. Our secondary goals include: (1) collection of DNA from EOAD participants for exploratory studies applying next generation sequencing; (2) collection and banking of clinical, biofluid and imaging measures for future research and sharing with the larger research community; and (3) establishing a network of EOAD sites that will enable future planning and implementation of clinical trials in EOAD. While the research is focused on EOAD, LEADS will also follow individuals who meet clinical criteria for MCI or dementia due to probable AD but have a negative amyloid PET scan (EOnonAD) with the goal to generate important scientific knowledge about this patient population.

Data collected in this study will address several significant gaps in AD research. In addition to affording this highly motivated population the chance to contribute to AD research, EOAD patients offer the opportunity to study a more “pure” form of AD with fewer age-related brain co-pathologies[1, 2].

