## 4.0 STUDY DESIGN AND INVESTIGATIONAL PLAN

The LEADS design builds on the success of two major natural history/biomarker initiatives in AD: ADNI and DIAN. Like those initiatives, the LEADS approach links longitudinal clinical and cognitive assessments with multiple imaging and biofluid markers that capture different elements of the AD pathophysiological cascade. Its alignment to ADNI will allow us to use ADNI LOAD participants as a disease comparison group.

LEADS is a non-randomized, natural history, non-treatment study. Approximately 850 cognitively impaired (EOAD and EOnonAD) participants and 100 CN participants will be enrolled at approximately 20 sites in the United States. Approximately 40 CI participants and 10 CN participants will be enrolled in sites outside of the U.S. as a part of iLEADS, the international expansion of LEADS. Clinical/cognitive, imaging, biomarker, and genetic characteristics will be assessed across the three cohorts: EOAD, EOnonAD, and CN.

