#### **7.4.2.1 Amyloid PET scanning**

Cognitively impaired and CN participants will undergo an amyloid PET scan as outlined in Appendix 1. The study staff will evaluate each participant prior to administration of tracer to determine if they are still suitable to undergo the scan (e.g., previous research PET scan exposure in the previous 12 months). For women of childbearing potential, a urine pregnancy test will be obtained and negative result confirmed on the day of scanning.

The screening scans for cognitively impaired participants only will be interpreted by the PET Core to assess amyloid status. The read will be based on a consensus between visual and quantitative assessments. Dichotomous visual interpretations of summed images will be performed by a qualified rater using validated criteria. Standardized Uptake Value Ratio (SUVR) images will be created using whole cerebellum as a reference region and a threshold SUVR will be used to define scan positivity. Scans in which visual and quantitative classifications that are incongruent will be arbitrated by consensus by at least two members of the PET Working Group.

Screening amyloid PET results for all cognitively impaired participants and M36 amyloid PET results, as applicable, for all EOnonAD participants, positive and negative, will be provided to sites. The Site PI or an affiliated study physician will be responsible for disclosing the results to the study participant and their family. The clinician should follow best practices in disclosing amyloid PET results. Whenever feasible, results should be disclosed in person. If an in-person disclosure is not feasible due to geographic distance or other factors, a telemedicine appointment could be considered a viable substitute. Disclosure of results by phone call only is discouraged but allowable at the discretion of the Site PI.

Longitudinal amyloid PET scans for the EOAD and EOnonAD cohorts will not receive an official read, however trans-axial images may be provided to the participant at the discretion of the site PI. See sections 7.4.2.2-7.4.2.5 below, as not all participants will complete longitudinal amyloid PET scans.

Amyloid PET scans from the CN cohort will not receive an official read and results will not be disclosed.

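### Exclusions 9 and 10 screen for trial enrolment and recent investigational agents, not for prior exposure, so an AD patient whose amyloid was lowered by treatment outside a trial can be enrolled as EOnonAD

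*Protocol*

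**What the plan says.** Section 5.2 lists two drug-related exclusions for the EOAD, EOnonAD and CN cohorts. Item 9 reads "Investigational agents are prohibited 30 days prior to entry". Item 10 reads "Previous enrollment in a therapeutic trial targeting amyloid or tau" and has no time limit. The last item, 18, is a general discretion: "Deemed ineligible by the Site PI for any other reason".

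Both impaired cohorts enter on a clinical criterion (section 5.1): "Meets NIA-AA criteria for MCI due to AD or probable AD dementia". Section 1.0 defines EOnonAD as people who meet the clinical criteria but whose amyloid PET is negative. Section 7.4.2.1 names the scan that decides this: "The screening scans for cognitively impaired participants only will be interpreted by the PET Core to assess amyloid status". The read combines a visual and a quantitative assessment, with arbitration if they disagree. Sections 7.4.2.3 to 7.4.2.5, on the alternative tracers, confirm that the screening scan is used for cohort assignment.

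Section 7.2 (Medication List) collects the medications being taken at each visit. Section 7.2 (Medical History) covers diseases, psychiatric history and substance use. Section 4.0 states the design: "LEADS is a non-randomized, natural history, non-treatment study".

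**The concern.** Item 10 asks whether a person was in a trial, not whether the person received an agent. Applied literally, it turns away someone who took placebo in an amyloid trial and admits someone who received an amyloid-targeting agent outside a trial. Because item 10 has no time limit, the protocol already treats a history with this class of agent as a permanent bar for new entrants. The wording simply does not reach everyone with that history.

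This matters because EOAD and EOnonAD are separated by amyloid status alone. H3c compares APOE4 carrier rates between the two cohorts. Aim 5 looks for non-AD causes in EOnonAD, in H5c by clustering clinical and biomarker data. AD patients with treated, lowered amyloid would carry AD genetics and AD clinical features into a cohort labelled non-AD. Treated patients who still read positive would go into EOAD, whose amyloid levels and rates of decline are compared with ADNI LOAD in H1b and H2a as natural history.

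**Working it through.** No figure in the protocol depends on this point, so there is none to reproduce. The check is to run each type of exposure through the stated rules.

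| History at screening | Item 9 | Item 10 | Result |
|---|---|---|---|
| Placebo arm of an amyloid or tau trial | not triggered | triggered | excluded |
| Active arm of such a trial | only if within 30 days | triggered | excluded |
| Investigational agent of this class outside a trial, within 30 days | triggered | not triggered | excluded |
| The same, more than 30 days earlier | not triggered | not triggered | eligible |
| Non-investigational agent of this class, any time | not triggered | not triggered | eligible |

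The last two rows are the gap; only item 18 stands in the way. For those patients, section 5.1 asks for clinical criteria, which a treated AD patient meets. Section 7.4.2.1 then reads the screening scan without reference to treatment history or an earlier positive scan. A negative read gives EOnonAD and a positive read gives EOAD.

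**Effect on H3c, for scale only.** Inputs:
- 650 EOAD and 200 EOnonAD (Synopsis).
- EOAD carrier rate 50%, taken from the approximate APOE4+ share used for Aim 3 in section 21.1.4. Section 2.0 puts the EOAD rate below 50%.
- True EOnonAD carrier rate p: assumed, 30% to 38%.
- Share c of EOnonAD who are amyloid-lowered AD cases: assumed, 0% to 20%. These cases are assumed to carry APOE4 at the EOAD rate.

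The observed EOnonAD rate is p_mix = p(1 − c) + 0.50c. The observed difference is therefore 0.50 − p_mix = (0.50 − p)(1 − c). For p = 0.35 and c = 0.10, p_mix = 0.315 + 0.05 = 0.365 and the difference is 0.135, against a true 0.15.

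Power is by the normal approximation, two-sided 0.05, with pooled variance under the null and unpooled under the alternative. The planned Fisher's exact test would give somewhat lower values.

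| p | c = 0 | c = 5% | c = 10% | c = 20% |
|---|---|---|---|---|
| 30% | 20.0 points, 99.9% | 19.0, 99.8% | 18.0, 99.6% | 16.0, 98.2% |
| 35% | 15.0 points, 96.6% | 14.25, 94.7% | 13.5, 92.3% | 12.0, 84.9% |
| 38% | 12.0 points, 84.9% | 11.4, 81.1% | 10.8, 76.6% | 9.6, 66.4% |

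The bias is proportional to c whatever p is. Loss of power matters only if the true difference is modest.

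**Can the existing data identify these cases?** Only in part. The medication list records current use, and the stated content of the medical history does not include past drugs. A course that ended before screening need not appear in either.

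**The case against.** **No documented frequency.** The protocol does not say that agents of this class are available outside trials, that any participant has taken one, or that one turns a scan negative. This stands. A headcount would require multiplying an assumed exposure rate by an assumed clearance rate, and the documents anchor neither. What remains is a gap in the wording of the rule, which does not depend on a frequency.

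**Other safeguards.** Most impaired participants have baseline tau PET, blood biomarkers are collected, a consensus panel reviews diagnosis at every visit, and EOnonAD participants have amyloid PET again at Month 36. A misassigned case may well be noticed. However, no stated rule uses any of these to set aside the screening assignment because of earlier treatment. Item 18 permits exclusion without requiring it, and about 25 sites (section 13.0) may use it differently.

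**Limited impact.** H3c keeps high power in much of the range shown, and the bias runs toward no difference, so it would not create a false H3c finding. Section 21.1.2 calls the EOnonAD analysis exploratory. All of this is fair. It limits the harm to H3c but does not help Aim 5, where the non-AD label is itself the subject of study.

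**Record rather than exclude.** Section 8.8 takes participants back after a therapeutic trial and asks about their trial involvement, so recording exposure is already an accepted model. That is a legitimate sponsor choice, but no equivalent question is stated for new entrants.

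**Washout.** A reader might infer that the entry and re-entry intervals contradict each other, because returning participants face a different one: "Investigational agents are prohibited for five half-lives prior to study re-entry". The documents do not support that. Item 10 bars new entrants from amyloid or tau trials permanently, whereas section 8.8 describes people coming back from a therapeutic trial. The two intervals serve different groups.

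**Conclusion.** The point holds as a flaw in the eligibility wording. Exclusions 9 and 10 leave open prior exposure to a non-investigational amyloid- or tau-targeting agent, and to an investigational one given outside a trial more than 30 days before entry. The cohort rule then has no means of separating treated AD from non-AD disease.

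The size is unknown. Given a contaminated share c and an EOAD-like carrier rate among those cases, the H3c difference shrinks by the factor (1 − c); the values of c and p in the table are assumptions. Two wider readings are not supported. The item names both amyloid and tau agents, so a reader might infer that either could move a patient into EOnonAD; misassignment requires an agent that lowers amyloid enough for a negative scan. A reader might also infer that data already collected are enough to find every exposed case, and section 7.2 does not show that. The change is worth making because it is cheap and protects the definition on which H3c and Aim 5 rest.

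**What to change.** 1. Reword exclusion 10 so that it covers any prior exposure to an amyloid- or tau-targeting agent, in or outside a trial, as well as trial enrolment. If the sponsor means to admit people exposed outside a trial, the protocol should say so and state how they are assigned to a cohort.
2. Add one screening question on past exposure to agents of this class, since the medication list captures only current use.
3. For participants already enrolled, identify exposed cases as far as records allow. Keep those who were exposed before screening and read amyloid-negative out of EOnonAD in H3c and Aim 5, at least as a sensitivity analysis.
4. Prescribe no washout on the strength of this point. At most, the sponsor should confirm that the different intervals for entry and re-entry in section 5.2 are intended.

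The cost is one amended criterion, one added question, a records check that may be incomplete, and the loss of some candidates. How many cannot be estimated from the documents.

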### **7.5.2 Peripheral Blood Collection for Genetic Testing**

All cognitively impaired individuals will have a 6 ml blood sample collected at the Baseline Visit. This sample will be sent to and stored in NCRAD and will be used for CLIA

confirmation of a known pathogenic mutation, if it is found. If a known pathogenic mutation is found, the CLIA laboratory will utilize the stored blood sample to confirm the mutation identified through the research studies. The availability of this sample will also allow a participant to consent to genetic testing results at any time during the study.

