### **7.6.2 Safety Laboratory Assessments**

Prior to lumbar puncture all participants will be subjected to the following safety labs. Safety labs will be conducted locally. However, if previous safety labs exist from a CLIA or appropriately certified laboratory within 60 days of LP, they can be used to review clinical significance and determine LP eligibility.

- complete blood count with differential (CBC w/diff)
- basic coagulation panel

The laboratory reports must be reviewed and signed and dated by the Site PI (or a medically-qualified individual delegated by the PI) prior to conducting the study LP.

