# **10.0 SIDE EFFECTS**

## **10.1 Lumbar Puncture**

The most common complications of LP consist of post-LP back pain and post-LP headache (PLPH). PLPH typically begins within three days after the procedure in most participants. If a participant develops typical PLPH, bed rest, adequate hydration, and simple analgesics should be started.

In a large multicenter LP study, 31% of participants reported post-LP complaints; however, these were mostly mild in nature. Severe complications were very rare [60].

Common side effects included:

- Back pain (17%)
- Headache (19%)
- Typical post-LP headache (PLPH) (9%)

Lower rates of post-LP headache were noted when atraumatic (Sprotte) needles were used. [61, 62] Sprotte needles will be used in this study.

Very rare (prevalence of <0.01%) but potential serious complications consist of post-LP infections, spinal and subdural cerebral hematoma, and cerebral venous thrombosis. In an effort to mitigate these risks, a trained clinician must perform the LP.

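### The platelet limit for the optional lumbar puncture is printed per ml, 1,000-fold below the same number per microlitre, so this one criterion would practically never be met

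*Protocol*

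**What the plan says.** Protocol Section 5.2 lists conditions that apply "For optional lumbar puncture procedure only" as exclusion item 17. Item 17a opens with a general rule: "Clinical laboratory values must be within normal limits or, if abnormal, must be judged to be not clinically significant by the Site PI". Three specific limits follow, of which the first is "Platelet count <100,000/ml". The other two concern INR and PT/PTT. Items 17b to 17d add procedural contraindications (including a history of a bleeding disorder), raised intracranial pressure and related lesions, and anticoagulant use.

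Section 7.6.2 names the tests done before LP: a "complete blood count with differential (CBC w/diff") and a basic coagulation panel, both run locally. It gives no platelet threshold. It also states: "The laboratory reports must be reviewed and signed and dated by the Site PI", or by a medically qualified delegate, before the LP takes place.

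Section 10.1 says of the LP that very rare but "potential serious complications consist of post-LP infections, spinal and subdural cerebral hematoma", together with cerebral venous thrombosis.

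**The concern.** The unit makes the limit far too low to select anyone. A platelet limit exists to pick out candidates whose bleeding risk should stop the puncture or at least prompt a decision about it. A limit of 100 platelets per microlitre lies below any count likely to be seen, including very severe thrombocytopenia, so item (i) is in effect switched off.

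The error runs in the unsafe direction, and Section 10.1 names the bleeding complications that the criterion should help to prevent. The criterion is also used repeatedly. Appendix 1 schedules safety labs and optional LP around screening and baseline, at Months 12, 24 and 36 for EOAD and EOnonAD participants, and at Month 24 for cognitively normal participants. Section 13.0 expects about 25 sites in the United States and abroad. A site whose laboratory reports in 10^9/L has to convert the printed limit, and a correct conversion gives 0.1 x 10^9/L.

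**Working it through.** The protocol derives no figure on this point, so there is nothing to reproduce. The check is a unit conversion.

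**Inputs**
- Printed limit: 100,000 per ml (Section 5.2, item 17a(i)).
- 1 ml = 1,000 microlitres; 1 L = 1,000 ml.
- Illustrative counts are assumptions, because the protocol gives none: 10,000 per microlitre (very severe thrombocytopenia), 50,000 per microlitre, and 150,000 to 450,000 per microlitre (normal range).

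**Printed limit in usual units**
- Per microlitre: 100,000 / 1,000 = 100.
- Per litre: 100,000 x 1,000 = 100,000,000 = 0.1 x 10^9/L.

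**Same number read per microlitre**
- Per ml: 100,000 x 1,000 = 100,000,000.
- Per litre: 100,000,000 x 1,000 = 100 x 10^9/L.
- Ratio to the printed limit: 100,000,000 / 100,000 = 1,000.

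**Assumed counts against the printed limit** (count per ml / 100,000)

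| Count per microlitre | Count per ml | Multiple of printed limit | Flagged as printed? | Flagged if per microlitre? |
|---|---|---|---|---|
| 10,000 | 10,000,000 | 100 | No | Yes |
| 50,000 | 50,000,000 | 500 | No | Yes |
| 150,000 | 150,000,000 | 1,500 | No | No |
| 450,000 | 450,000,000 | 4,500 | No | No |

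**Does anything else in the document correct the unit?** No. No other section states a platelet limit. Where the protocol writes ml elsewhere it means millilitre: in Section 7.5.2, "All cognitively impaired individuals will have a 6 ml blood sample collected at the Baseline Visit", and CSF volumes are given in ml in Sections 7.5.3 and 7.7.1.

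**Could the unit be a PDF-reading artefact?** The extracted text keeps other special characters: the Greek beta in the abbreviation list, the inequality signs in Sections 5.1 and 21.1.3, and the degree sign in Section 7.7.1. A micro sign that was simply dropped would leave /l, not /ml, so it would have to have been misread as the letter m. The text contains no micro sign elsewhere to test this against, so the possibility stays open.

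**The case against.** The strongest objection is that the sentence directly above the limit already covers the gap. On the assumed normal range, every count from 100 to 100,000 per microlitre is abnormal, so 17a sends it to the Site PI for judgement anyway. If items (i) to (iii) are flags under that sentence and not absolute bars, correcting the unit sends the same participant to the same decision-maker. Around this stand the signed laboratory review, the INR and PT/PTT limits, the bleeding-disorder and anticoagulant criteria, the Site PI's general discretion under item 18, the requirement in Section 10.1 that a trained clinician perform the LP, and the fact that the LP is optional. Harm would need a markedly low count, a site that reads the unit literally, and a physician who signs the report regardless. An experienced clinician would probably read the intended unit.

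Most of this stands, and it limits the consequence. It does not make the number right. A printed threshold is there so that judgement is exercised in the same way at all sites, and Section 7.6.2 expects the laboratory results to be used in deciding LP eligibility. A limit that flags no one cannot do that.

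The second objection, that the slip may come from the PDF reading, also stands in part. The uses of ml elsewhere are collection volumes, for which millilitre is the only sensible unit, so they do not settle what the source page shows here. Checking that page is therefore the first step.

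**Conclusion.** The concern holds: item 17a(i) is wrong as written. The printed limit equals 100 per microlitre (0.1 x 10^9/L), a factor of 1,000 below the same number per microlitre, and it fails to flag counts from 100 up to 100,000 per microlitre. The conversion is exact. That the criterion would practically never be met rests on assumed platelet counts, but it holds even at 10,000 per microlitre, which is 100 times the printed limit.

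The defect is confined to one threshold for an optional procedure. It does not touch study entry, endpoints, power or analysis, and other safeguards make actual harm unlikely; the document gives no frequency from which to estimate it. Confidence is medium because the text alone cannot exclude a misread micro sign. If the source page prints ml, the line should be corrected. If it shows a micro sign, the point falls away.

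**What to change.** 1. Check item 17a(i) on the source page for a micro sign.
2. If it prints ml, have the clinical lead confirm the intended limit.
3. At the next amendment, restate the item as a platelet count below 100,000 per microlitre (100 x 10^9/L). Giving both units spares sites a conversion.
4. Send sites a short note with the corrected limit.

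The cost is a unit change in one line and the note to sites. Design, data collection and analysis do not change.
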